### ***Maximum overall intensity***

Maximum intensity is derived from the daily intensities computed as described above in “Daily intensity” and is calculated as the maximum of the daily intensities over the period considered. The Grade of intensity is applied following the rules described in the Section 9.2.2.3.2 of the protocol.

### ***Presence***

Presence is derived from the maximum intensity of the period considered:

- No presence : None
- Presence : Grade 1, Grade 2 or Grade 3
- Unknown or Missing presence : Missing

Subjects with at least one non-missing presence for a specific endpoint will be included in the analysis. Conversely, those without a non-missing presence will not be included in the analysis of the endpoint.

### ***Time of onset***

Time of onset is derived from the daily intensities computed as described above in “Daily intensity.” It corresponds to the first day with intensity of Grade 1, Grade 2, or Grade 3.

Note: If a reaction is not continuous (i.e., reaction occurs over two separate period of time intervened by at least one daily intensity Missing or None) then the time of onset is the first day of the first occurrence.

**Table 9 – Categories for time of onset**

Injection Site Reactions (D0-D7)	Systemic Reactions (D0-D7)
D0-D3	D0-D3
D4-D7	D4-D7

***Number of days of occurrence***

Number of days of occurrence over the period considered is derived from the daily intensities computed as described above in “Daily intensity.” It corresponds to the number of days with daily intensities of Grade 1, Grade 2, or Grade 3. Number of days of occurrence on the solicited period with a specified intensity may also be derived.

**Table 10 – Categories for number of days of occurrence during the solicited period**

Injection Site Reactions (D0-D7)	Systemic Reactions (D0-D7)
1-3 days	1-3 days
4-7 days	4-7 days
8 days	8 days

***Overall number of days of occurrence***

If a reaction is ongoing at the end of the solicited period, then the overall number of days of occurrence is derived from the daily intensities and the stop date of the reaction after the end of the solicited period. The overall number of days of occurrence is:

$$\begin{aligned} & (\text{stop date} - \text{vaccination date}) \\ & + (\text{number of days of occurrence within the solicited period}) \\ & - \text{length of the solicited period} + 1 \end{aligned}$$

If the stop date is missing or incomplete (containing missing data [MD]), the overall number of days of occurrence will be considered as Missing.

**Table 11 – Categories for overall number of days of occurrence**

Injection Site Reactions	Systemic Reactions
1-3 days	1-3 days
4-7 days	4-7 days
≥8 days	≥8 days
Missing	Missing

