### **Solicited reactions**

The following summaries of solicited reactions within 7 days after vaccine injection will be presented using the terms prelisted in CRB:

- All and Grade 2 or 3 solicited reaction, solicited injection site reaction, and solicited systemic reaction
- Solicited reaction, each solicited injection site reaction (injection site pain, injection site erythema, injection site swelling, injection site induration, and injection site bruising), and solicited systemic reaction (fever, headache, malaise, myalgia, and shivering)

- Solicited injection site reactions (injection site pain, injection site erythema, injection site swelling, injection site induration, and injection site bruising) and solicited systemic reactions (fever, headache, malaise, myalgia, and shivering) by following category:
  - By maximum intensity
  - By time of onset period
  - By range of number of days of occurrence during the solicited period (for any solicited reaction and Grade 3 solicited reactions)
  - By range of overall number of days of occurrence for the reactions still ongoing at D8 after vaccine injection
  - By action taken

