### ***Ongoing***

Ongoing is derived from the last daily intensity of the solicited period computed as described above in “Daily intensity” and the maximum intensity on the ongoing period. The investigator’s ongoing flag is not used because the measurement would determine the ongoing status of the reaction.

Note: a reaction could be derived as not ongoing for the analysis despite being considered as ongoing by the investigator (e.g. when the maximum measurement after D7 for adults aged  $\geq 65$  years is  $>0$  mm but  $<25$  mm in adults). If the last daily intensity of the solicited period is at least Grade 1 and maximum intensity on the ongoing period is also at least Grade 1, then the reaction is considered ongoing. In any other cases the reaction will not be considered as ongoing.

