### ***Duration***

Duration is derived from the start and stop dates of the unsolicited non-serious AE provided in the clinical database:

Stop date of unsolicited non-serious AE – start date of unsolicited non-serious AE + 1

The duration should be considered as missing only if one or both of the start and stop dates of the unsolicited non-serious AE is missing or partially missing.

Duration will be displayed by period as following:

- 1-3 days
- 4-7 days
- 8-14 days
- $\geq 15$  days
- Missing

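### SAP Table 11 is filled only by solicited reactions still ongoing at D8, yet it puts every duration of 8 days or more in one open row

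*SAP*

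**What the plan says.** SAP 4.7.2 (Solicited reactions) lists, among the summaries of solicited reactions, one "By range of overall number of days of occurrence for the reactions still ongoing at D8 after vaccine injection". SAP 5.4.2.1 (Ongoing) counts a reaction as ongoing when the last daily intensity of the solicited period is at least Grade 1 and the "maximum intensity on the ongoing period is also at least Grade 1".

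For these reactions SAP 5.4.2.1 (Overall number of days of occurrence) states that the value "is derived from the daily intensities and the stop date of the reaction after the end of the solicited period". The formula takes the stop date minus the vaccination date, adds the "number of days of occurrence within the solicited period", subtracts the length of that period and adds 1. A missing or incomplete stop date makes the value Missing.

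Table 11, "Categories for overall number of days of occurrence", then groups the result as 1-3 days, 4-7 days, ≥8 days or Missing, for injection site and systemic reactions alike. Table 10, which covers days within D0-D7 only, has rows 1-3, 4-7 and 8 days.

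For unsolicited non-serious AEs, SAP 5.4.2.2 (Duration) has its own display rule, introduced by "Duration will be displayed by period as following". Its rows are 1-3, 4-7, 8-14, ≥15 days and Missing.

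**The concern.** A table restricted to reactions that outlast the diary period has one descriptive job: to show how long they went on. Its highest cut-point lies at 8 days, which is about where persistence past D7 begins. For a reaction that started on the day of vaccination or the day after and never paused, a known stop date adds nothing in this table to the fact that the reaction was ongoing at D8.

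If many persistent reactions start early, the two arms could differ markedly in how long reactions last after D7 and still show the same Table 11 percentages. The SAP lists no other by-arm summary of this quantity. The general rule in SAP 4.1 on means, medians and quartiles for continuous data does not clearly fill the gap. The same section presents clinical safety results as numbers and percentages of subjects, and SAP 4.7.2 asks for this variable by range.

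**Working it through.** **Inputs**
- Solicited period: D0 to D7 (SAP Table 10). Counting both ends, L = 8 days. This reproduces the top row of Table 10, 8 days.
- Earliest stop for a reaction in Table 11: D8, because the reaction must be Grade 1 or higher on D7 and again afterwards (SAP 5.4.2.1, Ongoing).
- End of scheduled follow-up: V02 at D28 to D35 (Protocol 5.1.4). Related AEs may be followed for longer (same section).

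**Formula.** With stop day t, counted from vaccination, and k days of Grade 1 or higher within D0-D7:

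overall days = t + k − L + 1 = t + k − 7.

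For an uninterrupted reaction with onset on day s, k = 8 − s, so overall days = t − s + 1.

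**Result by onset day, uninterrupted reactions**

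| Onset | Days if stop D8 | Row if stop D8 | First stop day in the ≥8 row | Days if stop D28 | Days if stop D35 |
|---|---|---|---|---|---|
| D0 | 9 | ≥8 | D8 | 29 | 36 |
| D1 | 8 | ≥8 | D8 | 28 | 35 |
| D2 | 7 | 4-7 | D9 | 27 | 34 |
| D3 | 6 | 4-7 | D10 | 26 | 33 |
| D4 | 5 | 4-7 | D11 | 25 | 32 |
| D5 | 4 | 4-7 | D12 | 24 | 31 |
| D6 | 3 | 1-3 | D13 | 23 | 30 |
| D7 | 2 | 1-3 | D14 | 22 | 29 |

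Onset on D0 or D1 always gives the ≥8 row. Onset on D2 to D7 gives it from the stop day in the fourth column onwards. Up to D35 the row spans 8 to 36 days.

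**Intermittent reactions.** With stop on D8 the value is k + 1, so a reaction with gaps and k ≤ 6 can fall in a lower row. If L were read as 7, each value would rise by 1, and onset on D0, D1 or D2 would always give the ≥8 row.

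**Share of reactions in the ≥8 row.** The documents give no onset or stop distribution, so the following rests on assumptions: uninterrupted reactions, known stop dates, and a constant daily probability of stopping from D8, taken as 0.8 down to 0.2. In the 90%, 70% and 50% scenarios, later onsets are spread evenly over D2-D7.

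| Assumed onset | Share in the ≥8 row |
|---|---|
| All on D0-D1 | 100% |
| 90% on D0-D1 | 90-95% |
| 70% on D0-D1 | 71-85% |
| 50% on D0-D1 | 52-75% |
| Uniform over D0-D7 | 28-62% |

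**Effect of splitting the row at 15 days.** A D0-onset reaction of t + 1 days falls in 8-14 for stops on D8 to D13, and in ≥15 from D14. A D1-onset reaction of t days falls in 8-14 for stops on D8 to D14, and in ≥15 from D15. The 9-day and 29-day cases are then separated.

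**The case against.** The strongest reply is that this is a choice of bin width in a table that the protocol does not require. The protocol endpoint (9.2.2.2) is number of days of occurrence for solicited reactions up to 7 days after vaccination, and Table 10 covers that range in full. Table 11 is an extra, safety is descriptive, and no hypothesis depends on it. The unsolicited-AE bands apply to a different variable (calendar duration, with no allowance for gaps), so the SAP is not inconsistent in using other rows here. A ≥15 row is open as well: reactions of 16 and 29 days would still look the same. All of this stands. It limits the importance of the point, but it does not give the present top row any power to describe persistence in early-onset reactions.

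A reader might also infer more than the documents support:
- *That almost every persistent reaction falls in the top row.* Of the 8 × 28 = 224 combinations of onset D0-D7 and stop D8-D35, 203 (91%) do. That counts calendar cells, not reactions, and weights a stop on D35 the same as one on D8. The assumed patterns above give anything from 28% to 100%, and missing stop dates have their own row.
- *That the stop dates are wasted.* The exact number of days is derived before grouping. Only the display loses it.
- *That the rows were carried over from Table 10.* They look alike, but Table 11 has an open top row and a Missing row, and nothing states how they were chosen.
- *That the protocol expects the arms to differ in persistence.* Protocol 1.3.2 expects a higher rate of injection site reactions by the SC route. It says nothing about duration. A difference in how many reactions outlast D7 would still show in the Table 11 counts.

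**Conclusion.** The point holds as a low-importance improvement. As planned, Table 11 cannot distinguish a reaction of about 9 days from one of about 4 weeks. This is certain for uninterrupted reactions with onset on D0 or D1 and a known stop date. It also applies to later-onset reactions unless they stop soon after D7, between D8 at the latest for D2 onset and D13 at the latest for D7 onset. It rests on L = 8, which Table 10 supports; L = 7 would widen the effect slightly.

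How many subjects are affected is unknown, because the number with a reaction ongoing at D8 and the onset and stop distributions are not in the documents. There is no error or contradiction in the plan, and no effect on the primary analysis, the analysis sets or any test.

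**What to change.** In SAP Table 11, for both injection site and systemic reactions, replace the row ≥8 days with two rows, 8-14 days and ≥15 days. Keep 1-3 days, 4-7 days and Missing. These are the bands of SAP 5.4.2.2 (Duration), so reactions that outlast the diary period would be described in the same bands as unsolicited non-serious AEs.

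The cost is a change of category labels in the SAP and in the table program. The derivation stays as it is and no further data are collected, since the stop date already enters the formula.

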### ***Ongoing***

Ongoing is derived from the last daily intensity of the solicited period computed as described above in “Daily intensity” and the maximum intensity on the ongoing period. The investigator’s ongoing flag is not used because the measurement would determine the ongoing status of the reaction.

Note: a reaction could be derived as not ongoing for the analysis despite being considered as ongoing by the investigator (e.g. when the maximum measurement after D7 for adults aged  $\geq 65$  years is  $>0$  mm but  $<25$  mm in adults). If the last daily intensity of the solicited period is at least Grade 1 and maximum intensity on the ongoing period is also at least Grade 1, then the reaction is considered ongoing. In any other cases the reaction will not be considered as ongoing.

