### **5.4.2 Data handling conventions for safety variables**

#### **5.4.2.1 *Solicited Reactions***

##### *Daily intensity*

All daily records for solicited reactions will be derived into daily intensity according to the following classification: None, Grade 1, Grade 2, Grade 3, or Missing. The category of Unknown will be considered Missing if Unknown is recorded.

For measurable injection site reaction (Erythema/Swelling/Induration/Bruising):

- Grade 1:  $\geq 25$  to  $\leq 50$  mm
- Grade 2:  $\geq 51$  to  $\leq 100$  mm
- Grade 3:  $> 100$  mm

For measurable systemic reactions (Fever):

- Grade 1:  $\geq 38.0$  to  $\leq 38.4$  °C, or  $\geq 100.4$  to  $\leq 101.1$  °C
- Grade 2:  $\geq 38.5$  to  $\leq 38.9$  °C, or  $\geq 101.2$  to  $\leq 102.0$  °C
- Grade 3:  $\geq 39.0$  °C, or  $\geq 102.1$  °C

For the derivation of daily intensities the following sequential steps will be applied:

For solicited reactions (except Fever/Pyrexia) with an investigator presence recorded as “No” and with all daily records missing, all daily intensities will be derived as “None”.

For non-measurable solicited reactions, daily intensities will correspond to daily records reported in the clinical database. For measurable solicited reactions the daily measurements reported in the clinical database will be converted based upon the intensity scales defined in the protocol; this assumes a reaction that is too large to measure (non-measurable, “NM”) is Grade 3. Note that the intensity could be considered as “None” (not a reaction) in the analysis despite being considered a reaction by the investigator (e.g., swelling measurement  $>0$  mm but  $<25$  mm in adults).

Note: The maximum intensity during the ongoing period is derived from the record of the maximum intensity/measurement after the end of the solicited period following the rule described above.

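### A missing Day 7 or post-Day 7 grade makes a solicited reaction 'not ongoing' in the SAP, so it drops out of the one table that reports duration beyond Day 7

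*SAP*

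**What the plan says.** SAP section 5.4.2.1 derives ongoing status from two grades. If the last daily grade of the solicited period is at least Grade 1 and the "maximum intensity on the ongoing period is also at least Grade 1, then the reaction is considered ongoing". For everything else: "In any other cases the reaction will not be considered as ongoing". The investigator's "ongoing flag is not used because the measurement would determine the ongoing status of the reaction". The example given there is a recorded size above 0 mm but below 25 mm, which the SAP deliberately treats as not ongoing.

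Under Daily intensity in the same section, the possible values are "None, Grade 1, Grade 2, Grade 3, or Missing. The category of Unknown will be considered Missing if Unknown is recorded". The only replacement of missing grades applies to reactions other than fever with investigator presence recorded as No "and with all daily records missing, all daily intensities will be derived as" None. For the later period, "The maximum intensity during the ongoing period is derived from the record of the maximum intensity/measurement after the end of the solicited period", with the same conversion rules. Nothing is said about that record being blank. SAP section 5.4.4.1 (Intensity) only refers back to Daily intensity.

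The status is then used for duration: "If a reaction is ongoing at the end of the solicited period, then the overall number of days of occurrence is derived" from the daily grades and the stop date. The output is listed in SAP section 4.7.2: "By range of overall number of days of occurrence for the reactions still ongoing at D8 after vaccine injection". Its categories in Table 11 include a Missing row, which serves for a missing or incomplete stop date.

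**The concern.** A blank grade says nothing about whether the reaction continued, but the residual clause turns it into a No. The reason given for ignoring the investigator's flag is that a measurement settles the matter. That supports overriding the flag when a value exists; it gives no reason to ignore the flag when the value is blank.

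The error runs one way. An indeterminate reaction may or may not have continued, and the rule always says it did not. A reader of the Day 8 table could not tell a resolved reaction from an unrecorded one. Elsewhere the SAP keeps such gaps visible or treats them cautiously: missing presence stays missing, a missing stop date gets its own row, and missing causality is counted as related.

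**Working it through.** The plan states no figure for this point, so there is none to reproduce. The check is an enumeration of the rule and a test of the duration formula.

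**Enumeration.** Each of the two grades (last solicited-period grade, maximum after Day 7) can be None, Grade 1, Grade 2, Grade 3 or Missing, giving 5 × 5 = 25 pairs.

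- Ongoing under the SAP: both at least Grade 1, 3 × 3 = 9 pairs.
- Not ongoing: 25 − 9 = 16 pairs.
- Pairs with at least one Missing: 5 + 5 − 1 = 9, all not ongoing.
- Of those 9, 2 contain a recorded None: (None, Missing) and (Missing, None). The two-grade rule already fails there, so not ongoing is correct on the SAP's own terms.
- The other 9 − 2 = 7 are indeterminate: (Grade 1, 2 or 3, Missing), (Missing, Grade 1, 2 or 3) and (Missing, Missing).

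If indeterminate pairs were labelled Missing, exactly these 7 would change; the 9 ongoing pairs and the remaining 9 not-ongoing pairs would stay as they are. The 7 of 25 counts logical combinations and is not a rate in subjects.

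**Duration formula** (SAP section 5.4.2.1): overall days = (stop date − vaccination date) + days of occurrence in the solicited period − length of that period + 1. Day 0 to Day 7 has length 8. A fully recorded reaction from Day 0 to Day 12 gives 12 + 8 − 8 + 1 = 13 days, which is right. The maximum grade after Day 7 is not an input.

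**Two illustrative records, both with a stop date of Day 12:**

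| Record | SAP status | Table 10 (solicited period) | Overall days if treated as ongoing | Table 11 |
|---|---|---|---|---|
| Grade 1 on Day 0 to Day 7; grade after Day 7 missing | Not ongoing | 8 days | 12 + 8 − 8 + 1 = 13 | Absent; would be ≥8 days |
| Grade 1 on Day 0 to Day 6; Day 7 missing; Grade 1 after Day 7 | Not ongoing | 7 days (4-7 row) | 12 + 7 − 8 + 1 = 12 | Absent; would be ≥8 days |

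In both, the duration can be calculated from data the SAP already uses, yet the reaction appears in no row of Table 11.

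**Reach.** Presence, maximum intensity, time of onset and days of occurrence within Day 0 to Day 7 are each derived from the daily grades and do not use ongoing status. The overall-days table is the only listed output that does.

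**The case against.** A reader might infer that the SAP undercounts solicited reactions generally, or that reactions lasting past Day 7 are recorded as ended throughout the safety report. The documents do not support this. Only the overall-days table uses the status, and the first record above still appears in the top row of Table 10. The safety endpoint in protocol section 9.2.2.2 is the number of days of occurrence for reactions up to 7 days after vaccination; no separate endpoint for duration beyond Day 7 is named.

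A reader might also infer that the rule cannot work for pain, headache, malaise, myalgia and shivering, because they are not measured. That goes too far: the SAP uses the recorded maximum intensity or measurement after Day 7, so a recorded grade does the same job for these five. Only the blank case fails. Nor is the rule strictly a replacement of missing data. The grade itself stays Missing, and the derived status is what becomes definite.

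It would be tempting to let the flag decide whenever any grade is missing. That would wrongly set ongoing to Yes in the 2 pairs with a recorded None, including a size below 25 mm, which the SAP excludes on purpose.

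Two further objections stand in part. Reading the last daily intensity as the last non-missing one would rescue a blank Day 7, but the text does not say so, and a blank after Day 7 would remain. Diary gaps are to be clarified with the subject (protocol section 13.2), and consistency checks and queries apply (protocol section 11.2). These limit how often the problem arises but do not change what happens when it does.

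**Conclusion.** The point holds, with minor severity. On the plain text, a solicited reaction with a missing Day 7 or post-Day 7 grade and no recorded None is classed as not ongoing and leaves the overall-days table without entering its Missing row. Persistence shown in that table can only be lowered as a result. Day 0 to Day 7 results are unaffected, safety is descriptive with no testing planned, and the primary immunogenicity conclusion is untouched.

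The size cannot be calculated, because the documents give no rate of missing grades. Given the clarification and query procedures, it is probably small. The conclusion assumes that Missing falls under the residual clause, which does not use that word, and that the last daily intensity means the Day 7 value.

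**What to change.** Add a short rule to SAP section 5.4.2.1 (Ongoing):

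1. When both grades are recorded, keep the present rule.
2. When either recorded grade is None, keep not ongoing, whatever the flag says.
3. When a grade is missing and no recorded grade is None, for the subject-graded reactions (pain, headache, malaise, myalgia, shivering): set ongoing to Yes if the investigator's flag is Yes or a stop date after Day 7 is recorded. Derive overall days from the stop date with the existing formula.
4. In the same situation for the measured reactions (erythema, swelling, induration, bruising, fever), where a blank could hide a value below Grade 1, set the status to Missing. Do the same for any reaction with neither a flag nor a stop date. Show these in the Missing row of Table 11.

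The SAP's own text indicates that the flag and stop date are already collected, so no new data are needed. The cost is a few lines of SAP text and slightly more programming; a few reactions would move into the ongoing or Missing rows.

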#### **5.4.2.2 Unsolicited Non-serious AEs**

Unsolicited AEs include non-serious unsolicited AEs and SAEs. This subsection only covers the endpoints for unsolicited non-serious AEs.

